C.8. Randomization. The Efron ('biased coin') procedure¹³⁹ will be used to assure near-equal sample sizes and good representation on three variables of interest (gender, age $<$ or $>$ 80 years, and NPW speed $<$ or $>$ 70 cm/s¹³⁷) in both groups. Also see C.15.e. It will not be efficient to randomize by more categories. Besides, variables such as illness are highly correlated with speed and age, and are dealt analytically as covariates. Group assignment will be dispensed in sealed opaque envelopes generated by [name] using sequential study numbers so that the assistant who enrolls the participants will be blinded to randomization assignment of the next participant until assigned. [name] will not be involved with subject testing or interventions.

C.9. Sample size. We will enroll **420 seniors (210 per group)**. Power and assumptions in section C.14.1.

[figure not shown]

Figure 3. Subject Flow

C.10. Blinding. Given the nature of our interventions, double-blinding both subjects and testers will not be feasible. But we will include a number of methods (besides randomization) to reduce bias.

- Selection bias will be reduced by concealing treatment allocation until the subject is entered into trial.¹⁴⁰
- Primary outcome is an objective endpoint (gait speed/SPPB) and not subjective mobility complaints.¹⁴⁰
- C-REM and health control interventions will be done in different sites and at non-overlapping times.
- The assessment team (and location) will be separate from intervention team.
- Participants and study staff will be instructed not to disclose group assignment or details of interventions.
- **Post-intervention questionnaire** (C.12.5) to assess maintenance of blinding.

C.11. Interventions. Both interventions will be given 3 times weekly for 8 weeks without crossover. C-REM program is supervised by [name] and the health education control by [name]. A **manual of operations** for all study activities will be developed during study setup (see **Table 3** in E.2.). Our intervention is based on a social cognitive model that views health behavior as being acquired and maintained through a complex set of behavioral, cognitive, and environmental conditions. Social cognitive theory concepts will be combined with strategies derived from applications of the Transtheoretical Model to mobility interventions^{59, 141} (e.g., consciousness raising early in the program; reinforcement management later in the program).^{59, 142}

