- c. **Leisure and CHAMPS physical activity scales¹³⁰** will be used to measure leisure and physical activities post-intervention. This will enable us to monitor lifestyle changes that may be related to C-REM.
- d. **Post-intervention questionnaire** will be administered to both groups to assess maintenance of blinding.
- e. **Health literacy questionnaires¹⁸⁹** will be given pre- and post-intervention in both groups. This will serve as a process measure for the efficacy of our health education intervention in the control group.

C.13. TIMELINE. We propose to screen and intervene in 210 subjects per group (assuming 20% attrition); 24-26 subjects will be randomized at a time into C-REM or health education programs (17 cycles over 54 months). We have recruited and evaluated larger samples in our other aging studies. Screening will start in month 2, and the interventions in month 4. A planned interim analysis by the DSMB (E.8.) will be conducted when 210 subjects are accrued (month 27 – Table 3). The final intervention group will have their post-intervention assessment in month 51. We will extend data collection to month 57 to enable us to collect outcomes to test durability till 12 months for the final intervention group. Detailed timetable with milestones and goals is in E.2.

C.14. DATA ANALYSIS.

Analytical Overview: Our goal in this preliminary RCT is to define the role of C-REM on improving simple and complex locomotion in sedentary frail seniors. Baseline distribution of covariates will be compared to assess adequacy of randomization to produce comparable groups of participants using appropriate graphical procedures and summary statistics.

C.14.1.a. Primary outcomes analysis: We will employ linear mixed effects model to compare the changes in gait speed and SPPB scores (P1) at post-intervention (week 9) as well as at 6 and 12 months post-intervention in C-REM versus controls.¹⁹³ The variance will be allowed to differ between C-REM and controls. The primary comparison between the two groups is post-intervention change in gait speed during NPW and WWT conditions and on SPPB. For WWT, we will also consider percent change in WWT speed from normal walking (*dual task cost*). We can define improvers on NPW and WWT by using cutscores on these measures as done in our pilot study (see C.14.2 and ref²⁶), and compare proportion of improvers vs. non-improvers in the two groups using generalized linear mixed effects models.¹⁹³

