Nonetheless, given our sample size we can explore any gender based intervention effects in our study. We shall adjust for gender and conduct gender-stratified analysis.

- **Covariates:** The following pre-specified set of baseline covariates^{21, 25, 191} were selected to determine their influence on the treatment: age, gender, education, chronic illnesses, cognitive test performance, pain, arthritis and cardiac fitness.¹⁷⁸ This method is preferred to adjusting for covariates that are imbalanced between treatment groups using significance testing, because it is possible for a covariate to have a strong confounding effect even if the difference in the average value of that variable between the parallel arms is not significant.¹⁹² We will also monitor any change in these measures over the intervention period and analytically account for their effects by including these measures (baseline levels as well as change) in linear mixed effect models to account for possible confounding.
- Adjusting for performance on baseline **cognitive tests** and stratified analysis by baseline cognitive status in the C-REM group will be done.
- Our **dual-task procedures** have been replicated and validated in many published papers.^{4, 13, 24, 29, 75} We recognize that participants may employ, despite the standardized instructions, different strategies when dual-tasking. In the context of the linear mixed effects models, we will examine whether performance and decline on the cognitive interference task (reciting alternate letters of the alphabet alone and in WWT) was related to dual-task costs observed on the primary walking task and will interpret the results accordingly.

C.14.1.b. Power for primary outcome: The primary hypothesis examines change in gait speed (during NPW and WWT conditions) and SPPB. Improvement in speed is ~10 cm/s after 8-12 week PE interventions.^{41, 46, 79, 80} In contrast, gait speed in the non-intervention controls show minimal improvement,⁷⁹ unchanged,⁴⁶ or declined.^{41, 80} Based on these PE effects and our pilot study,²⁶ we conservatively estimate a 5 cm/s improvement post-C-REM, which is ~50% of the mobility effect in PE trials and less than that achieved in our pilot study (**8 cm/s**). This magnitude of change also corresponds to that recommended as small but clinically meaningful change in gait in aging studies.^{10, 11}

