The sample size (420) provides >80% power to detect clinically meaningful differences at significance level of 0.05. The conservative Bonferroni correction for multiple testing was used in sample size calculations. Based on conservatively estimated SDs of 12 cm/s, 20 cm/s and 1.5 points for NPW, WWT and SPPB, respectively, to detect clinically meaningful differences of 5 cm/s for NPW and 0.5 points for SPPB with 80% power,^{10, 11} and a conservatively estimated 10 cm/s for WWT (16 cm/s WWT speed improvement in our pilot study¹³), at least 169 subjects per group are needed. To take account the projected 20% drop out rate at end of intervention, 210 subjects per group will be enrolled.

5 cm/s is the minimal detectable intervention change that we can study with 80% power, and is not the maximal threshold of change expected after C-REM in this RCT. Any improvement >5 cm/s by C-REM will increase power. For instance, we observed **8 cm/s** improvement in our pilot study²⁶ ('substantial improvement' range^{136, 193}), which will provide us >90% power to test our hypothesis in this RCT.

Durability: Assuming cumulative dropout rates of 25% at 6 months, with n=210 per group, we will have 92%, 99% and 75% power for detecting differences of 5cm/sec, 10 cm/s and 0.5 points in NPW, WWT and SPPB, respectively. At 1 year of follow-up, assuming 30% cumulative dropout, we will have 90%, 98% and 72% power

for detecting differences of 5 cm/sec, 10 cm/s and 0.5 points in NPW, WWT and SPPB, respectively. If the difference in SPPB is substantial (1 point), the power will be more than 95% at both time points. However, given the lower power to reliably estimate SPPB change, we designate the durability examination as an exploratory aim. We will seek additional funding to extend examination of durability.

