C.14.2.b. Tertiary outcome: In addition to PFC oxygenation levels on fNIRS, alternative measures such as areas activated, bilateral versus unilateral activation, and any reduction in activation will be considered simultaneously using linear mixed effects model.¹⁹³ There is limited data to reliably estimate power for the tertiary outcome (fNIRS). Nonetheless, the sample of 420 should provide adequate power to examine this outcome. In our pilot study we were able to demonstrate significant cross-sectional differences in prefrontal activation on fNIRS during WWT and NPW conditions in 11 older and 11 younger persons.²⁶ While we have major cross-sectional experience in administering fNIRS in large aging samples, we do not have experience in longitudinal fNIRS data. Hence, this tertiary prediction is exploratory and should help generate hypotheses.

C.15. Potential pitfalls and solutions.

- a. **Missing data.** Losses to follow-up can be classified into non-informative (missing at random) and informative censoring (drop out depends on the unobserved outcomes). No adjustment is necessary for non-informative censoring. However, for informative censoring, parameter estimates and resulting tests on hypotheses will be biased without further adjustment. The best way to handle missing data is to avoid it. However, we recognize that despite all our efforts (see C.11.5), there will be missing data.
- b. **Dropouts:** We will follow-up with participants who dropped out of the study to determine both their mobility status¹²⁰ and reasons for withdrawal. We now propose intention to treat analysis (C.14.1.a). A rich set of telephone-based information (T-MAQ¹²⁰) will be collected even for those subjects who may drop out. We will utilize this auxiliary information to assess the MAR assumption and combine it into the main model through joint modeling and multiple imputation approaches.²⁰³ [name] has applied these approaches to eliminate or reduce bias in presence of informative censoring in our other aging studies.²⁰¹
- c. **Regression to mean.** To parse out the effects of treatment versus regression we utilize a primary outcome (gait speed/SPPB) with high reliability, a control group, and will analytically examine this effect.
- d. **Confounders.** To account for key confounders such as age, sex, and gait speed, we propose to use block randomization. Baseline cognitive/physical/ cardiac fitness will be accounted in our analysis.

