- e. **Speed ≤70 cm/s.** We will use this widely used slow gait cutscore as one of our randomization variables.¹⁵⁰ If we exclude all with slow gait we may bias against enrolling oldest subjects who have mean gait speeds that are lower than the 70 cm/s cutscore.³⁰ We will stratify analysis by this cutscore and examine effects.
- f. **Feasibility.** In our pilot study,¹³ 50% of subjects met Fried frailty criteria⁴³ but completed interventions. We propose to over-enroll by 20% to account for any attrition. We have incorporated multiple methods to promote adherence and reduce possibility of missing data. We have also built in stopping rules.
- g. **Which aspects of the cognitive training are responsible for improvements?** While it is important to show that the overall C-REM program improves mobility; Mindfit also tracks training patterns that will help us refine the C-REM program for future studies. The availability of such extensive data will enable us to

develop individual and/or group models of growth using techniques such as growth curve analysis. One can also investigate the relation between growth patterns on tasks and mobility benefits. Dose is also studied.

h. Negative findings: We will employ several strategies to assess potential negative findings. 1) We showed that the protective effect of attention/EF against decline in gait speed is moderated by cognitive reserve.⁶ We will evaluate whether cognitive reserve moderates the effect of C-REM on mobility; 2) We will apply for additional funding to establish a bio-repository for this cohort. This will provide an opportunity to evaluate whether genetic factors or biomarkers such as brain derived neurotrophic factor (BDNF) may mediate the effect of C-REM on mobility.²⁰⁸⁻²¹⁰ 3) We have the opportunity to examine C-REM effects on other mobility, cognitive, mood, and psychosocial outcomes.

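### The primary model is not said to adjust for the baseline value of its own outcome or for the 70 cm/s randomisation factor; adding both costs nothing and helps mainly SPPB

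*Combined protocol and SAP*

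**What the plan says.** - **C.14.1.a, primary outcomes analysis.** A linear mixed effects model compares changes at week 9, 6 months and 12 months. "The primary comparison between the two groups is post-intervention change in gait speed during NPW and WWT conditions and on SPPB." The text does not say whether baseline is a covariate, one of the repeated responses, or a response with a common mean across arms.
- **C.14.1.a, Covariates.** The pre-specified baseline set is "age, gender, education, chronic illnesses, cognitive test performance, pain, arthritis and cardiac fitness". A later sentence adds baseline levels and changes of these same measures to the mixed models. It refers back to the listed covariates, so it does not bring in baseline NPW, WWT or SPPB.
- **C.8.** Allocation uses a biased coin to secure "good representation on three variables of interest": gender, age split at 80 years, and NPW speed split at 70 cm/s. Age and gender are in the covariate list; NPW speed is not.
- **C.15.e**, on the 70 cm/s cutscore: "We will stratify analysis by this cutscore and examine effects."
- **C.15.d** names gait speed as a key confounder, deals with it through randomisation, and adds: "Baseline cognitive/physical/ cardiac fitness will be accounted in our analysis." The physical component is not defined.
- **C.15.c** says regression to the mean will be examined analytically and names no method.
- **C.14.1.b**: "The sample size (420) provides >80% power to detect clinically meaningful differences at significance level of 0.05."

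**The concern.** In a randomised trial a baseline-adjusted comparison is never less precise than an unadjusted change score, and it is more precise whenever change depends on baseline. Here it probably does. Participants enter through an SPPB ceiling and a gait-speed ceiling, and both are primary measures. With equal variances, the correlation between change and baseline is -sqrt((1-rho)/2), which is -0.22 at rho 0.9 and -0.39 at rho 0.7.

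Adjustment also guards against chance imbalance. Of the three outcomes only NPW is balanced by design, and only at one cut point. The pilot (B.5.c) shows the pattern on another measure: on the executive attention score the C-REM arm started worse (203 against 132 ms) and improved more (to 164, against 125 ms).

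At stake is power on SPPB, the outcome that drives the sample size and has none to spare. Two analysts could also follow this text and fit different primary models.

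**Working it through.** **Inputs.** From C.14.1.b: differences of 5 cm/s (NPW), 10 cm/s (WWT) and 0.5 points (SPPB); SDs of 12, 20 and 1.5; 80% power; 169 needed per group; 210 enrolled; 20% dropout, so 210 × 0.8 = 168. Assumed: two-sided tests; the SDs are SDs of change (the pilot's NPW change SDs, 11.4 and 6.8 cm/s, fit this); the baseline to week-9 correlation rho, which the documents do not give. C.12.1 reports test-retest reliability above 0.9 for NPW and 0.935 for WWT, but these are not 8-week correlations in trial-eligible people.

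**1. The plan's own figure.** The text says Bonferroni was used but not for how many tests. For SPPB, n per group = 2 × (1.5/0.5)² × (z_alpha + 0.8416)².
- At 0.05/2, z_alpha = 2.2414 and n = 18 × 9.505 = 171.1, so 172. This is within 3% of 169.
- At 0.05/3, n = 189, which does not match.

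Two-sided 0.025 also gives the stated durability powers for NPW, WWT and SPPB to within 2 points: 92.7/98.6/76.3% at 6 months (stated 92/99/75) and 90.8/98.0/73.1% at 12 months (stated 90/98/72). I use 0.025 below.

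**2. Variance ratio.** With a common variance s² at both times:
- unadjusted change: 2s²(1 − rho)
- baseline-adjusted: s²(1 − rho²)
- ratio: (1 + rho)/2, which is 0.95 at rho 0.9 and 0.85 at rho 0.7.

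Simulated NPW trials (168 per group, assumed baseline mean 75 cm/s) gave 0.967 and 0.848, in reasonable agreement.

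**3. Power with 168 per group, two-sided 0.025.** Power = Phi(difference / (SD × sqrt(ratio) × sqrt(2/168)) − 2.2414). For SPPB the first term is 3.055 unadjusted, 3.134 at ratio 0.95 and 3.314 at ratio 0.85.

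| Outcome | Unadjusted change | rho 0.9 | rho 0.7 |
|---|---|---|---|
| NPW | 94.3% | 95.3% | 97.1% |
| WWT | 99.0% | 99.3% | 99.7% |
| SPPB | 79.2% | 81.4% | 85.8% |

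For SPPB the required n per group falls from 172 to 163 (rho 0.9) or 146 (rho 0.7).

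**4. If selection shrinks the baseline variance.** Let entry criteria reduce the baseline variance by a factor k, leaving the regression slope unchanged, with rho the correlation before selection. The ratio becomes (1 − rho²) / [(1 − rho²) + k(1 − rho)²] = (1 + rho) / [(1 + rho) + k(1 − rho)]. For an illustrative, assumed k = 0.5:
- rho 0.9: 1.9/1.95 = 0.974, SPPB power 80.3%
- rho 0.7: 1.7/1.85 = 0.919, SPPB power 82.8%

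**5. What the 70 cm/s factor adds.** In the same NPW simulations, adding only the factor to a change-score model gave a ratio of 0.98 (rho 0.9) or 0.91 (rho 0.7). Adding it to a model that already held continuous baseline NPW changed nothing material (0.971 against 0.967; 0.851 against 0.848).

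**The case against.** The strongest reply is that the covariate sentence is not the plan's whole statement on baseline. C.15.e promises analysis stratified by the 70 cm/s cutscore, C.15.d promises to account for baseline physical fitness, and C.15.c promises to look at regression to the mean. A reader might infer that the NPW factor is absent from the analysis altogether; C.15.e rules that out. What remains is narrower. C.15.e reads most naturally as a look at effects by subgroup, C.15.d does not name its variable, and neither is tied to the primary model.

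A reader might also infer that precision is definitely lost on all three primary outcomes. The documents do not support that either. A mixed model with baseline among the responses and a common baseline mean would recover about the same efficiency as adjustment, and C.14.1.a leaves that option open. With a separate baseline mean in each arm and complete data, however, the contrast is the unadjusted difference in change, and the text permits that equally.

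The size is uncertain too, and this part of the objection stands. At the reliabilities the protocol quotes, the saving is only about 3% to 5% of variance, and no passage supports a particular lower rho. Listed covariates may absorb part of it, since C.8 says illness is highly correlated with speed and age. NPW and WWT have little power left to gain.

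Finally, this is not a validity problem. Leaving out a balancing factor tends to make standard errors conservative; it does not bias the estimate or inflate the type I error.

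**Conclusion.** The point holds as a free improvement. As written, the plan allows a primary analysis that uses neither the baseline value of the outcome nor the NPW randomisation factor, although both are collected before randomisation. The practical gain is mainly on SPPB: about 2 points of power at rho 0.9 and 6 to 7 points at rho 0.7, from 79.2%. It is smaller if entry criteria narrow the baseline spread (about 1 to 4 points in the k = 0.5 illustration) or if the listed covariates already carry some of the information. These figures rest on an assumed rho, change-score SDs, two-sided 0.025 and 168 completers per group. That the list omits these terms is certain from the text; the size of the gain is not.

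**What to change.** In C.14.1.a, state that each primary model includes the continuous baseline value of its own outcome, or is a mixed model with baseline means constrained to be equal across arms. State that each also includes the three randomisation factors as randomised: gender, age split at 80, and NPW split at 70 cm/s. In the NPW model the 70 cm/s factor adds essentially nothing once continuous baseline NPW is present; keeping it there is for consistency with the design. Then reconcile the covariate list with C.15.d and C.15.e: define baseline physical fitness, and say whether the stratified analysis is the primary model or a subgroup analysis.

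The cost is wording in the analysis plan. No new data, visits or participants are needed.

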Protocol: fNIRS recordings are conducted under four conditions: rest, NPW, talking (recite alternate letters) and WWT. See the Equipment section and our published studies¹⁶ for further details of fNIRS procedures. Activation patterns reported as difference between standing baseline and NW, and NW vs. WWT. We selected HbO₂ **concentration** as a marker of cortical activity because it is the most sensitive indicator of mobility related changes.^{168, 172} There are considerable individual differences in task-related changes in deoxyHb levels.¹⁷³ To avoid these problems, HbO₂ data from each channel is normalized by linear transformation. This normalization is also useful for circumventing the influence of differential path lengths among the subjects and that of cortical regions on the HbO₂ levels.¹⁷² fNIRS hardware supervision and signal processing will be conducted by Dr. [name] and Dr. [name] respectively, as done in our published and ongoing studies.¹⁶

Feasibility: The fNIRS was successfully implemented in our pilot study.¹⁶ In a population-based study to examine cognitive control mechanisms of mobility (1R01 AG036921-01A1, PI: [name]), we conducted fNIRS studies in NPW and WWT conditions in ~250 individuals in one year (cf. 420 in 5 years in this proposal).

We have administered fNIRS to more adults than reported in previous aging samples, but acknowledge that we have not yet defined longitudinal changes to establish fNIRS as a biomarker. Hence, this tertiary prediction is exploratory and should help generate hypotheses as well as provide insights into C-REM effects.

C.12.4. OTHER MEASURES: The effect of C-REM will be assessed on these additional measures. They also serve to define the baseline characteristics of the groups, assess confounding, and as covariates in analyses.

- a. **Other Cognitive:** Standard tests to determine cognitive status, rule out dementia and as process measures for C-REM. Test battery not described due to space limitations but are available in our referenced papers.^{20, 102, 103} These tests will enable examination of C-REM effects on cognition. If funded, we will seek supplementary grants to study effects of C-REM on cognitive decline.
- b. **Duke Activity Status Index**¹⁷⁴ will be used to adjust for baseline cardiac fitness.
- c. **Pain and fatigue scales.**^{175 176-178}
- d. **Handgrip/quadriceps strength.**^{10, 177}

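### C.14.1.a puts post-randomisation change in cognition, pain and cardiac fitness into the mixed models as confounding control, without saying that these models are not the primary analysis

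*Combined protocol and SAP*

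**What the plan says.** C.14.1.a states the target as follows: "The primary comparison between the two groups is post-intervention change in gait speed during NPW and WWT conditions and on SPPB". That sentence names no covariates. The method is a linear mixed effects model. The analysis is by intention to treat, which the section describes as unbiased for the effect of the intervention.

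The Covariates bullet opens with "The following pre-specified set of baseline covariates" and lists "age, gender, education, chronic illnesses, cognitive test performance, pain, arthritis and cardiac fitness". It ends by saying that change in these measures over the intervention period will be monitored and accounted for "by including these measures (baseline levels as well as change) in linear mixed effect models to account for possible confounding".

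Other places speak of baseline adjustment. The next bullet reads "Adjusting for performance on baseline cognitive tests and stratified analysis by baseline cognitive status in the C-REM group will be done". In C.12.4 the Duke index "will be used to adjust for baseline cardiac fitness". B.5.c and C.15.d also refer to baseline cognition or fitness.

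On the role of change in these measures:
- Prediction P2.2 in the Specific Aims is that C-REM improves executive function (EF), attention and processing speed.
- B.4 predicts that this improvement will in turn improve walking.
- The Mediation analysis bullet of C.14.1.a names change in attention and EF as a possible mediator of the effect on gait speed.
- C.12.4 covers the other cognitive tests, the cardiac fitness index and the pain scales, and says of them: "The effect of C-REM will be assessed on these additional measures".

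**The concern.** A confounder must be able to influence which arm a participant is in. Change that occurs after randomisation cannot do so. It can, however, be a consequence of the arm, and adjusting for a consequence of treatment alters what the treatment coefficient means.

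For cognition the plan takes both positions within one section: the change is a mediator in one bullet and a source of confounding in another. If a model with that term were used for efficacy, the coefficient would be the part of the effect that does not run through measured cognition. Even that part could be biased by unmeasured common causes of cognitive and gait change. The better C-REM worked as hypothesised, the more of its effect such a model would tend to remove.

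The plan also leaves open which model is primary. An unadjusted model, a baseline-adjusted model and one with baseline plus change terms all fit the text. The first two target the total effect; the third does not. Without a rule, the choice can be made after the data are seen.

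**Working it through.** **Reproducing the plan's power.** C.14.1.b gives SDs of 12 cm/s (normal pace walking, NPW), 20 cm/s (walking while talking, WWT) and 1.5 points (SPPB), with differences of 5, 10 and 0.5. It applies a Bonferroni correction but does not state the number of tests. Two-sided 0.025 matches best. With 25% dropout (n = 157 per arm) power is 92.4/98.5/75.8%, against the stated 92/99/75. With 30% dropout (n = 147) it is 90.6/97.9/72.7%, against 90/98/72. I therefore use 0.025.

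**NPW without a change term.** n = 210 × 0.8 = 168 per arm.
- SE = 12 × √(2/168) = 1.309
- 5/1.309 = 3.82; 3.82 − 2.24 = 1.58; power is 94%.

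**NPW with change in cognition in the model.** Two inputs are assumptions, because the documents give neither:
- a = shift in cognitive change caused by C-REM, in SD units;
- r = within-arm correlation of cognitive change with gait change.

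The total effect is held at 5 cm/s. The within-arm slope of gait change on cognitive change is 12r, so:
- adjusted coefficient = 5 − 12ar
- SE = 12 × √(1 − r²) × √[(2/168)(1 + a²/4)]

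For a = r = 0.3 the coefficient is 5 − 1.08 = 3.92 and the SE is 1.263. Then 3.92/1.263 = 3.10 and 3.10 − 2.24 = 0.86, which gives about 80% power (80.3% by noncentral t). A simulation of 4,000 trials gave 3.90 cm/s and 80.4%.

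Coefficient (cm/s) and power (noncentral t, two-sided 0.025):

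| a | r = 0.1 | r = 0.3 | r = 0.5 |
|---|---|---|---|
| 0.1 | 4.88; 93.1% | 4.64; 92.7% | 4.40; 94.7% |
| 0.3 | 4.64; 89.8% | 3.92; 80.3% | 3.20; 70.5% |
| 0.5 | 4.40; 84.7% | 3.20; 59.3% | 2.00; 29.6% |

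At two-sided 0.05, which a closed testing procedure can allow, power is 96.8% without the term and 87.2% at a = r = 0.3.

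**Direction.** With a = 0.3 and r = −0.3 the coefficient rises to 6.08 cm/s. With no true gait effect and a = r = 0.3, the coefficient is −1.08 cm/s and the rejection rate is 8.3% at a nominal 2.5%. Of that, 8.2 points favour control and 0.1 favours C-REM.

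**The case against.** The strongest reply is that the sentence describes an additional analysis. It begins by saying that change will also be monitored. It sits among bullets on dose, mediation, gender strata and dual-task strategy, which are ancillary. The primary comparison is stated without covariates, and the section commits to intention to treat. This reading is possible. But the sentence says that the change terms will be included, gives confounding control as the purpose and uses the same model class as the primary analysis, and no label marks it as supplementary.

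Four stronger readings are tempting, and the documents do not support them:
- **That the plan breaks its own baseline-only rule.** No section says baseline only. The change terms are added to a baseline list, and C.12.4 lets its measures serve as covariates without restricting them to baseline values.
- **That the primary estimate will be distorted.** This follows only if the change terms enter the primary model, which the documents do not say outright.
- **That pain and cardiac fitness are mediators like cognition.** No section predicts that C-REM changes them; C.12.4 says only that effects will be assessed. For cognition, the listed covariate is general test performance and the named mediators are attention and EF. These overlap (C.12.4 calls the other cognitive tests process measures for C-REM), but they are not stated to be the same.
- **That the effect would be wholly removed, or efficacy falsely claimed.** B.7 allows a direct motor route, so attenuation need not be complete. In the null example above, nearly all excess rejections favour control.

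**Conclusion.** The point holds. As written, the plan has a rule that calls post-randomisation change a confounder and puts it into the mixed models. An efficacy model that follows the rule for cognition does not estimate the intention-to-treat effect. For pain and cardiac fitness the objection is narrower: the change is measured after randomisation and may be affected by treatment. Whether the primary estimate is affected depends on which reading of the unlabelled sentence is applied.

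The size is not known. The calculation covers NPW only and rests on assumed a and r. Over the ranges shown, power with the change term runs from about 95% to 30%, against 94% without it. The loss is trivial at a 0.1 SD shift and material from about 0.3 SD with moderate correlation. The case for correction rests on the estimand, not on these figures.

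**What to change.** In C.14.1.a:
- State that the primary efficacy models for NPW, WWT and SPPB use only the pre-specified baseline covariates and contain no post-randomisation change terms.
- Keep change in attention, EF and the psychosocial measures (depression or mood, self-esteem, self-efficacy) for the mediation analysis already planned in that section.
- Label any other change-adjusted model exploratory, and remove the description of it as confounding control.

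The cost is a few sentences of wording. No new data and no change in sample size are needed. The change should be made before treatment-group results are seen.
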